Primary SA1: Determine whether 24 weeks of GnRH_{AG} therapy causes a decline in physical activity when compared with placebo. Change in physical activity energy expenditure (PAEE) from baseline will be measured after 12 (secondary outcome) and 24 wk (primary outcome) of GnRH_{AG} vs placebo therapy. PAEE will be the difference between total daily EE (TEE) measured by the doubly-labeled water technique (DLW) and sleeping EE (SEE) measured by indirect calorimetry, adjusted for the thermic effect of feeding (TEF).¹⁴

H1: PAEE will decrease significantly after 12 and 24 weeks of GnRH_{AG} therapy when compared with placebo.

Secondary SA2: Determine the effects of gonadal function on multiple components of energy expenditure under free-living (DLW) and controlled (metabolic chamber) conditions, including 1) 24-h TEE measured by DLW, and 2) resting EE (REE), SEE, and TEF measured by indirect calorimetry in a metabolic chamber.

H2: When compared with placebo, GnRH_{AG} therapy will cause a decrease in TEE. The relative contributions of REE, SEE, TEF, and PAEE to the decline in TEE will be evaluated.

Secondary SA3: Determine whether the disruption of energy balance in response to GnRH_{AG} therapy leads to unfavorable changes in biomarkers of disease risk, including adiposity, insulin resistance, and inflammation. This will include the measurement of biomarkers in adipose tissue samples.

H3: When compared with placebo, GnRH_{AG} therapy will cause increases in adiposity, insulin resistance, and fasted serum inflammatory cytokines.

Secondary SA4: Because programmed exercise mitigates metabolic consequences of gonadectomy in animals, we will determine whether the bioenergetic and metabolic consequences of GnRH_{AG} in women can be

mitigated through a programmed, supervised exercise intervention (GnRH_{AG} vs GnRH_{AG}+exercise).

H4: Programmed exercise will attenuate the decrease in TEE and the increases in adiposity, insulin resistance, and inflammatory cytokines.

Exploratory Aim: To evaluate the effects of chronic sex hormone suppression and exercise on arterial stiffness and endothelial function. This preliminary data will be used for a new grant application examining the effects of exercise on modulating vascular function in E2-deficient women.

2. Research Strategy

2.a. Significance

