
2.d. Research methods

2.d.1. Overview

This will be a randomized, double-blinded (to the extent possible), placebo-controlled intervention to determine whether the suppression of ovarian function with GnRH_{AG} disrupts energy balance by causing a decrease in PAEE. Secondary aims are to determine the effects of the suppression of ovarian function on other components of energy expenditure and on biomarkers of disease risk and whether the consequences of GnRH_{AG} can be mitigated through programmed exercise. Participants will be women who are nearing the menopausal transition based on age (42-52 y) but have normal menstrual cycle function. They will be randomized to receive monthly injections of placebo or GnRH_{AG} (leuprolide acetate, 3.75 mg) for 24 weeks. Women who receive GnRH_{AG} will be further randomized to no exercise or a supervised exercise program. Thus, the 3 treatment arms are: placebo, GnRH_{AG}, GnRH_{AG}+exercise. Although a 2x2 study design (placebo vs drug; no exercise vs exercise) was considered, this was not feasible given the resources available under the grant mechanism.

2.d.2. Outcome variables

The primary outcome (Aim 1) will be PAEE after 24 weeks of intervention. PAEE will be the difference between TEE measured by DLW and SEE and TEF, measured by indirect calorimetry. It will be assessed at baseline and after 12 and 24 weeks of intervention. The **rationale** for PAEE as the primary outcome is the dramatic decrease in PA in response to OVX in laboratory animals (Fig 1), which could be a primary trigger for subsequent changes in adiposity and metabolic function. This will be the first controlled intervention trial to determine whether an objective measure of PA decreases in response to the suppression of ovarian function in women. GnRH_{AG} therapy for 4 months or longer increases fat mass and decrease fat-free mass (FFM).^{9,10,36} One concern is that women may begin to adopt compensatory behavioral changes (e.g., decreased food intake, increased physical activity) if changes in body composition are sensed. Thus, the greatest **biologically-mediated** decrease in PAEE may occur at the intermediate testing interval (12 weeks), before measurable changes in body composition are expected to occur; this will be the primary study endpoint.

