Limitation of the follow-up testing schedule. For women assigned to the placebo treatment arm, the follow-up tests will not necessarily occur at the same point in the menstrual cycle as the baseline test. Testing will occur during specific time intervals (weeks 10-12, 22-24) to be consistent with the GnRH_{AG} arms. Because this may increase the variance of changes in bioenergetics in the placebo arm, the sample size calculations relied on conservative assumptions (e.g., ability to detect a 25% change in PAEE; use of $\rho = 0.9$; power of 95%).

2.d.10. Data analysis

General Analysis Plan. Data analysis will occur in 4 steps: **1)** Descriptive analyses (including boxplots, scatterplots, profile plots to examine change over time) will be conducted for quality assurance and to assess need for data transformation; **2)** demographic and baseline characteristics of the groups will be compared; **3)** primary and secondary analyses will be completed; and **4)** findings will be assessed for their robustness to issues including the effects of any imbalances in important baseline covariates and the effects of missing data.

Primary Analysis. The primary analysis (**SA1**) will be an intention-to-treat comparison of the differences in the change in PAEE measured after 12 weeks of placebo or GnRH_{AG} therapy. This comparison will be conditioned on the stratification variable, age group (40-46, 47-60y). Statistical inference regarding the difference between treatment groups will be based on the estimated coefficient for a treatment group indicator variable in a linear regression model with 24-week change from baseline as the response variable, and explanatory variables,

including treatment group, age group, and baseline PAEE; the latter is included to improve the precision/power of the inference about treatment differences. The conclusion about statistical significance will be drawn from the linear contrast comparing the placebo and GnRH_{AG} groups.

Secondary Analyses. To address **SA2** and **SA3**, 24-week differences in other outcome measures (24-h TEE, REE, SEE, TEF, PA by accelerometry, measurement of biomarkers in adipose tissue samples, glucose and insulin response to OGTT, serum concentrations of

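### The primary endpoint is stated as both the 12-week and the 24-week change in PAEE, even within the primary-analysis paragraph, so the confirmatory test is not fixed

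*Combined protocol and SAP*

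**What the plan says.** Five statements in the combined protocol and SAP give a week for the primary endpoint, change in physical activity energy expenditure (PAEE) on GnRH agonist versus placebo.

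For 24 weeks:
- Section 1, Primary SA1: change in PAEE "will be measured after 12 (secondary outcome) and 24 wk (primary outcome").
- Section 2.d.2, first sentence: "The primary outcome (Aim 1) will be PAEE after 24 weeks of intervention".
- Section 2.d.10, Primary Analysis, the model that carries the inference: a "linear regression model with 24-week change from baseline as the response variable".

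For 12 weeks:
- Section 2.d.2, last sentence, on the 12-week interval: "before measurable changes in body composition are expected to occur; this will be the primary study endpoint".
- Section 2.d.10, Primary Analysis, first sentence: an "intention-to-treat comparison of the differences in the change in PAEE measured after 12 weeks of placebo or GnRH_{AG} therapy".

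H1 predicts a significant fall at both weeks and does not order them. Section 2.d.4 powers the trial for a difference in change in PAEE without naming a week. The last paragraph of 2.d.10 places the 12- and 24-week time course among the secondary analyses but does not say which week is primary.

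**The concern.** The contrast (placebo versus GnRH agonist), the model and the covariates are fixed. The response variable is not. The comparison declared primary uses one week and the regression that decides it uses the other, so the paragraph cannot be carried out as written.

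The two weeks cannot be treated as interchangeable. Section 2.d.2 argues that women may begin to compensate once they sense changes in body composition, so that the largest biologically driven fall in PAEE may be seen at 12 weeks. Section 2.d.9.2 repeats the argument. The protocol therefore allows for an effect at 12 weeks that has faded by 24, and in that case the choice of week decides whether the trial is positive.

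Two things are at stake. Two competent analysts could report different primary results from the same data. And since either week can be supported from the text after the results are known, the 0.05 level given for the primary test is not protected.

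**Working it through.** **1. Can the sample size settle the week?** Inputs from 2.d.4: baseline PAEE 800 kcal, SD 330 kcal, effect 25%, pre-post correlation 0.90, 15 per group in three groups, level 0.05 (sidedness not stated; two-sided assumed).

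- Difference: 0.25 × 800 = 200 kcal/d.
- SD of change: √[2(1 − 0.90)] × 330 = 147.6, given as 148.
- Noncentrality: 200 / (148 × √(2/15)) = 3.70.
- Power from the noncentral t: 94.6% with 28 df (two-group t test), 95.1% with 42 df (three-group ANOVA contrast).

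The stated 95% is reproduced. No input is tied to a week, so the calculation fits either reading and does not resolve the conflict.

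**2. The statements side by side**

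| Place | Primary week |
|---|---|
| 1, Primary SA1 | 24 |
| 2.d.2, first sentence | 24 |
| 2.d.2, last sentence | 12 |
| 2.d.10 Primary Analysis, first sentence | 12 |
| 2.d.10 Primary Analysis, regression response | 24 |

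Three say 24 and two say 12. Sections 2.d.2 and 2.d.10 each contain both. No sentence ranks them or sets a testing order.

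**3. Size of the consequence if either week could count as success.** The plan does not state such a rule; this shows what the ambiguity would permit. The error rate depends on the correlation r between the two test statistics, which the documents do not give. Assume first that the plan's 0.90 holds between every pair of the three visits (baseline, week 12, week 24):

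- Unadjusted change scores: r = (0.90 − 0.90 − 0.90 + 1) / [2(1 − 0.90)] = 0.10 / 0.20 = 0.50.
- Adjusted for baseline, as in the planned regression: r = (0.90 − 0.81) / (1 − 0.81) = 0.474.

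The 0.50 follows from the equal-correlation assumption, whatever the common value. The 0.90 enters only the adjusted figure.

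The probability that at least one |Z| exceeds 1.96 under the null, from the bivariate normal:

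| r | Type I error |
|---|---|
| 0 (ceiling) | 0.0975 |
| 0.3 | 0.0951 |
| 0.474 | 0.0915 |
| 0.5 | 0.0907 |
| 0.7 | 0.0835 |
| 0.9 | 0.0704 |

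Two other correlation patterns stay inside this range:

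- Adjacent visits 0.90, baseline to week 24 0.81. Unadjusted r = 0.19 / √(0.20 × 0.38) = 0.69; adjusted r = 0.171 / √(0.19 × 0.3439) = 0.67. Error 0.084 to 0.085.
- Weeks 12 and 24 correlated 0.98, both 0.90 with baseline. Unadjusted r = 0.18 / 0.20 = 0.90; adjusted r = 0.17 / 0.19 = 0.89. Error 0.070 to 0.071.

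**The case against.** The best defence is that the plan leans clearly to 24 weeks. SA1 carries the only explicit primary and secondary labels. Only one inferential model is written out, and its response is the 24-week change. The SA2 and SA3 outcomes are analysed as 24-week differences by the same method. On this view the 12-week wording is a leftover that an analyst following the model sentence would pass over.

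That supports choosing 24 weeks in the repair, but it does not remove the conflict. The 12-week sentence in 2.d.2 has its own scientific argument, repeated in 2.d.9.2, so it is not evidently a typing slip. The other 12-week statement is the sentence that defines the primary analysis.

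A second objection is that 0.091 describes a scenario and not a rule in the plan, and that the correlation behind it is assumed. This is correct. The figure should be read as part of a conditional range of about 0.07 to 0.095. The contradiction itself does not depend on it.

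Third, 2.d.10 says the time trajectory and the biological consistency of the secondary outcomes will be examined to guard against false positives. These are matters of judgement. They set neither an alpha split nor a testing order, and they presuppose a primary endpoint that is already fixed.

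**Conclusion.** The concern holds. The current text names two different weeks for the primary endpoint, twice within a single section, and nothing else in the document decides between them. This is a contradiction in the rule that decides the trial, which is more than a missing detail, and it must be fixed.

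The type I error under an either-week reading is about 0.091, and 0.070 to 0.095 for correlations from 0.9 down to 0.3, against a nominal 0.05. That rests on three assumptions: two-sided tests, success allowed at either week without adjustment, and a correlation between the two changes that the documents do not supply. The finding that the primary week is not fixed needs none of them.

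**What to change.** Before unblinding, make the 24-week change in PAEE the single primary endpoint everywhere, in line with SA1, the first sentence of 2.d.2 and the regression model:

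- In the first sentence of the Primary Analysis (2.d.10), replace 12 weeks with 24 weeks.
- In the last sentence of 2.d.2, delete the closing clause that makes the 12-week interval the primary endpoint. The compensation argument can stay as the reason for measuring at 12 weeks.
- State that the 12-week change is a named secondary endpoint and cannot replace a non-significant 24-week result.
- For consistency, give the ranking in H1 and name the week in 2.d.4.

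If the sponsor prefers 12 weeks on its own rationale, the same requirement applies: one week, stated everywhere, before the data are seen. If both were wanted with either able to succeed, a split to 0.025 each would give 90.2% to 91.1% power per test at 15 per group. Restoring 95% would need 18 evaluable per group, still below the 22 to be enrolled.

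The cost is a wording amendment, chiefly in 2.d.2 and 2.d.10. Sample size, power and alpha stay as stated, and no new data or participants are needed. The document does not give the trial's status. If unblinded data have already been seen, the report should disclose the conflict and show both weeks.

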Other secondary outcomes of the study will include: 24-h TEE measured by DLW; REE, SEE, and TEF measured by indirect calorimetry in a metabolic chamber; energy intake estimated from food records; physical activity measured by accelerometry; body composition measured by dual-energy x-ray absorptiometry (DXA); glucose and insulin responses to an OGTT; serum concentrations of inflammatory cytokines (IL-6, hsCRP); and biomarkers in adipose tissue samples.

2.d.3. Study population

Volunteers will be women nearing the menopausal transition, based on age (40 to 60 y), with normal menstrual cycle function. The **rationale** for this approach was driven by the observation that a menopause-related decline in PA likely begins 3 to 4 years before menopause (Fig 6). We chose not to focus the study on women with perimenopausal symptoms for two reasons: 1) we may miss part of the perimenopause-related change in PAEE, and 2) the irregularity of menstrual cycles during the perimenopause complicates the scheduling of baseline tests around menstrual cycle phase. Specific inclusion and exclusion criteria are in Section 3.1.a.

2.d.4. Sample size justification

The expected effect of ovarian hormone suppression on PAEE was conservatively set at -25%, based on the range of decreases in physical activity observed in preclinical studies of -30% to -80% (Fig 1) and the decrease

of -50% in the prospective cohort study of women undergoing natural menopause.¹² Baseline PAEE was assumed to be 800 kcal with a SD of 330 kcal.⁶⁵ The variance of the difference between PAEE_{pre} and PAEE_{post} is $2(1-\rho)\sigma^2$. Using a conservative value of 0.90 for ρ (actual value, 0.98)⁶² and assuming no change in variance as PAEE decreases, the SD of the change will be 148 kcal/d. Based on the analysis plan to conduct a 1-way ANOVA with two contrasts (placebo vs GnRH_{AG}; GnRH_{AG} vs GnRH_{AG}+exercise), a sample size of 15 in each of 3 groups will achieve 95% power for either test to detect a 200 kcal/d difference between two groups in the change in PAEE using a *t* test at the 0.05 significance level. To account for attrition, we will enroll 22 per group.

2.d.5. Screening procedures

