Injections will be administered in a blinded manner, but participants on GnRH_{AG} will likely know their drug assignment because of the induction of amenorrhea. For this reason, volunteers will not be informed during the consenting process that the primary aim of the study is to determine whether GnRH_{AG} causes a decline in physical activity (i.e., such knowledge may change behavior). Rather, women will be informed that the loss of normal ovarian function may alter how the body uses energy or have other metabolic effects. Participants who do not tolerate GnRH_{AG} therapy can refuse further treatment after each monthly dosing. Among the first 64 premenopausal women treated with GnRH_{AG} in the PI's ongoing study (AG018198), this occurred only once. Participants who undergo at least 2 months of therapy but not 6 months will be asked to undergo testing at the end of their final month of therapy. Should this occur, data analyses will include covariate analysis to adjust for duration of intervention.

Exercise intervention. If the loss of ovarian function generates a biological drive toward sedentary behavior, it may be possible to override this through programmed exercise. In laboratory animals, E₂ add-back and programmed exercise (i.e., treadmill running) each prevented, to a large extent, the OVX-related changes in body composition and biomarkers of disease risk (Fig 5).²⁵⁻²⁹ The intent of **SA4** is to determine whether programmed exercise can offset the decline in PAEE in response to GnRH_{AG} (PAEE: GnRH_{AG} < GnRH_{AG}+exercise). Although it may seem logical to assume this will occur, it is possible that programmed exercise will cause a further decrease in other physical activities, such that programmed exercise produces no net gain in PAEE.

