inflammatory cytokines, and body composition will be analyzed as above. Secondary analyses will be evaluated for their consistency with the conclusions on the primary endpoint. We anticipate that changes in the secondary outcomes will be consistent (i.e., in terms of biological plausibility) with changes in the primary outcome so that significant differences in the primary endpoint will be reinforced by the secondary analyses. Failure to find biological consistency in primary and secondary endpoints will be taken as evidence that the effects of hormone suppression are not clear and that further study is necessary to resolve inconsistencies. This approach will reduce the risk of false-positive conclusions resulting from multiple statistical tests. **SA4** will be evaluated by ANCOVA as described above, regressing change in PAEE or REE on baseline, age group, and treatment group, adding a linear contrast to compare the GnRH_{AG} and GnRH_{AG}+exercise groups.

Exploratory Aim. Will be evaluated by ANCOVA as described above, regressing change in vascular outcomes (arterial stiffness or FMD) on baseline and treatment group, adding a linear contrast to compare the GnRH_{AG} and GnRH_{AG}+exercise groups.

The characteristics of the time trajectory (at 12 and 24 weeks) for treatment effects will also be determined in secondary analyses. These analyses will evaluate the biological plausibility of the time trajectory (i.e., a biologically-meaningful time trend) to rule out false positive conclusions in the primary analysis. Evaluation of the time trajectory will also motivate future studies of mechanisms and methods to improve longer-term outcomes. The analytic methods to be used for evaluation of the time trajectory include a mixed-effects model with time as a fixed covariate to estimate the mean effect at each measurement time,⁹³ conditioned on the stratification variable and the baseline value of the outcome variable.

2.d.11. Data management

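### The intention-to-treat primary regression gives a woman with a 12-week but no 24-week PAEE no defined route in, although a mixed model that would use her 12-week value is already planned as secondary

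*Combined protocol and SAP*

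**What the plan says.** The primary analysis (2.d.10, Primary Analysis) "will be an intention-to-treat comparison of the differences in the change in PAEE". Inference rests on the treatment coefficient in "a linear regression model with 24-week change from baseline as the response variable", with treatment group, age group and baseline PAEE as explanatory variables. That paragraph defines no analysis set and gives no method for a missing response.

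Other parts of the document bear on the same question:

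- **2.d.7, Drug intervention.** Women with "at least 2 months of therapy but not 6 months will be asked to undergo testing at the end of their final month"; if this happens, analyses are to adjust for how long the intervention lasted.
- **2.d.10, General Analysis Plan, step 4.** Robustness to missing data will be examined. No method is named.
- **2.d.10, last paragraph.** The time trajectory at 12 and 24 weeks will be studied with "a mixed-effects model with time as a fixed covariate to estimate the mean effect" at each visit, conditioned on the stratum and the baseline value. This is a secondary analysis.
- **2.d.4.** Power is computed for 15 women per group, and then "To account for attrition, we will enroll 22 per group".
- **Primary week.** SA1 in section 1 measures change "after 12 (secondary outcome) and 24 wk (primary outcome"). Section 2.d.2 opens with 24 weeks but ends by choosing the 12-week test, "before measurable changes in body composition are expected to occur; this will be the primary study endpoint". Section 2.d.10 describes an "intention-to-treat comparison of the differences in the change in PAEE measured after 12 weeks of placebo" or active therapy, and then models the 24-week change.

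**The concern.** A regression on one change score needs that change score. A woman measured at baseline and week 12 but not at week 24 contributes nothing to it unless some rule supplies her value. Without such a rule, the test described as intention-to-treat could in practice be run on women with a 24-week measurement only. That estimate is unbiased only if, given the model's covariates, being measured at week 24 is unrelated to response. A likelihood-based mixed model needs the weaker condition that loss depends on values already observed, including the week-12 PAEE. The SA2 and SA3 outcomes and the SA4 comparison are analysed in the same way, so they inherit the gap.

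**Working it through.** **1. Reproduce the plan's figure.** Inputs from 2.d.4: difference 200 kcal/d, SD 330, correlation 0.90, alpha 0.05 (taken as two-sided), 15 per group.

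- SD of change = √(2 × (1 − 0.90)) × 330 = 147.6, which the plan rounds to 148.
- Standard error = 148 × √(2/15) = 54.0; 200/54.0 = 3.70; 3.70 − 1.96 = 1.74, so power is 95.9%. With the t distribution it is 95.1% (three-group error, 42 df) or 94.6% (two groups, 28 df).

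The stated 95% reproduces.

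**2. Loss allowed for and loss seen.** Going from 22 to 15 allows 7/22 = 31.8%. The similar study in 2.c lost 7/64 = 10.9%. At that rate 22 × (1 − 0.109) = 19.6 per group remain, with power of about 98–99%. Power is not the issue.

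**3. Does 2.d.7 close the gap?** Set beside 2.d.10, it does not:

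- The early final test is not said to stand in for the 24-week value.
- The duration covariate is absent from the primary model.
- Duration of intervention is determined after randomisation, so adjusting for it does not fit an intention-to-treat comparison.
- The test is requested only after at least 2 months of therapy. A woman who leaves without it has no route in.
- Section 2.d.9.2 cites advice that serial doubly-labeled water measurements be at least 10 weeks apart. A woman tested at weeks 10–12 who stops at week 16 would be retested after 4–6 weeks, while the primary model has no place for her 12-week value.

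**4. Precision gain.** Let m be the fraction missing at week 24, all with a week-12 value (the best case), and r the correlation between the 12- and 24-week changes.

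- Completers only: s²/(n(1 − m)).
- Using the 12-week values: (s²/n)[1 + (m/(1 − m))(1 − r²)].
- Ratio of the second to the first: 1 − m r².

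The documents do not give r. If all visits are equally correlated at 0.90 (an assumption), the raw changes have r = (1 − 0.90)/(2 × (1 − 0.90)) = 0.5. After baseline adjustment, r = (0.90 − 0.81)/(1 − 0.81) = 0.47.

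| m | r = 0.47 | r = 0.5 | r = 0.7 | r = 0.85 |
|---|---|---|---|---|
| 0.32 | 0.93 | 0.92 | 0.84 | 0.77 |
| 0.11 | 0.98 | 0.97 | 0.95 | 0.92 |

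The first two columns are tied to the plan's own correlation. At 32% loss they are worth roughly 15/0.93 to 15/0.92, that is 16.1 to 16.3 women per arm in place of 15. The last two columns show the range if the two follow-up visits are more alike.

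**5. Bias.** A simulation (6,000 trials per row; placebo vs GnRH agonist, 22 per arm) used equal correlation 0.90, SD 330 and a true difference of −200 at both visits. Every lost woman has a 12-week value. In the response-dependent rows, the log-odds of loss in the GnRH arm rise by 1 for each additional 148 kcal/d of fall at week 12. That slope is an assumption with no source in the documents.

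| Loss setting | Dropout | 24-week regression | Using 12-week values |
|---|---|---|---|
| 10.9% | completely random | −200 (SE 46.3) | −201 (SE 45.9) |
| 10.9% | depends on 12-week fall | −193 (SE 47.3) | −201 (SE 46.7) |
| 31.8% | completely random | −200 (SE 54.8) | −200 (SE 52.8) |
| 31.8% | depends on 12-week fall | −181 (SE 54.9) | −200 (SE 53.8) |

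The regression's power at 31.8% is 94% under random loss and 89% under response-dependent loss. Its bias in the response-dependent rows is 200 − 193 = 7 and 200 − 181 = 19 kcal/d.

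**The case against.** A reader might infer that every woman without a 24-week value is dropped. The documents do not support that. The early final test and duration covariate in 2.d.7 show that the investigators meant to keep women treated for 2 to under 6 months, and step 4 of 2.d.10 promises a look at missing data. Both count. But neither is carried into the primary model, and a later robustness check leaves the primary estimate as it was.

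A reader might also infer that the losses will be women who tolerate the drug poorly or whose activity has already fallen. The only evidence supplied points elsewhere. Of the 7 women lost in the similar study (2.c), 1 left for side effects, 2 for lack of time and 4 for family problems. All women in that study received GnRH agonist and some had estradiol add-back, so it is an imperfect guide. Still, nothing in the documents links loss to falling PAEE.

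The primary week matters too. If week 12 governs, women lost between weeks 12 and 24 already have their primary value, and the mixed model recovers little for them.

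Finally, covariance-adjusted regression as primary with a mixed model as secondary is an accepted arrangement. A model with only two fixed visits also has no natural place for off-schedule final tests. That last point stands, so any change must include a rule for those tests.

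**Conclusion.** The point holds in limited form. As written, the intention-to-treat label is not backed by a rule for a woman who has a 12-week but no 24-week PAEE, and 2.d.7 does not supply one.

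The likely size is modest. Variance falls about 7–8% at the 32% allowance and about 3% at 11% loss, assuming equally correlated visits at 0.90 and a 12-week value for every lost woman. The bias avoided is about 19 kcal/d (roughly 10% of the 200 kcal/d effect) or 7 kcal/d, under the assumed response-dependent dropout only, and nil if dropout is completely random. The planned sample size is unaffected. The change is worth making because the dropout mechanism cannot be known in advance, the mixed model needs the weaker assumption, and it is already in the plan.

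**What to change.** 1. Reconcile the primary week across SA1, 2.d.2 and 2.d.10.
2. Make the planned mixed model the primary analysis: PAEE change at weeks 12 and 24, time as a category, treatment-by-time interaction, baseline PAEE and age stratum, unstructured covariance, and a small-sample degrees-of-freedom correction. Include all randomised women with any follow-up PAEE, and state this as the analysis set.
3. Take the placebo vs GnRH agonist contrast at the primary week from that model, without the duration covariate. The same model serves whichever week is chosen.
4. State how an off-schedule early final test is assigned to a visit.
5. Keep the single-time-point regression and the duration-adjusted analysis as named sensitivity analyses, which gives step 4 of 2.d.10 some content.

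The cost is analysis wording and a few lines of code, with no change to sample size, visits or participant burden. The downside is slightly more modelling. Women with no follow-up PAEE at all still contribute nothing, and the text should say so.
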